Appendix 5: Healthcare-Professional Reported Outcome Measures

2. If all atezolizumab IV infusions are switched to atezolizumab SC injections, please indicate how strongly you agree or disagree with each of the following statements¹. When answering question 3, please only consider atezolizumab IV and atezolizumab SC and not other IV treatment options.

	One "X" only					
	Strongly Disagree	Disagree	Neutral	Agree	Strongly Agree	Not applicable
a. Staff will have increased availability for other tasks in the pharmacy (e.g. reconstituting other drugs, performing more frequent or timely inventory checks, more timely responses to queries from other departments, etc.)						
b. Administrative procedures around atezolizumab SC will require less time (i.e. worksheet, release form, labels, etc.)						
c. Atezolizumab SC formulations will provide more flexibility for pharmacy staff in managing their workload						
d. Due to ready-to-use, atezolizumab SC formulations, potential dosing errors will be avoided						
e. Due to ready-to-use atezolizumab SC formulations, there will be less drug wastage (e.g. IV bag already reconstituted but not used, or not used/leftover drug in IV vial)						
f. Without having to reconstitute the drug, less storage space for atezolizumab SC related supplies will be required in the pharmacy						
g. Preparation procedures and associated time staff time commitment will be reduced						
h. It will ease drug administration for patients with difficult venous access						
Please use this box to add any additional comments you have:						

1. Statements are hypotheses and not actual claims

Appendix 5: Healthcare-Professional Reported Outcome Measures

Looking back over the atezolizumab drug preparation sessions, please indicate which administration method:

3. Was quickest from start to end of preparation to finish of administration (excluding observation period)

Atezolizumab IV Atezolizumab SC no difference

4. Required less resource use for preparation and administration, for example nursing time, facility costs, equipment, etc.?

Atezolizumab IV Atezolizumab SC no difference

Appendix 6 EuroQol EQ-5D-5L

Do not reproduce or distribute. The Sponsor will provide sites with all instruments to be completed in this study.

Under each heading, please check the ONE box that best describes your health TODAY.

MOBILITY

- I have no problems walking
- I have slight problems walking
- I have moderate problems walking
- I have severe problems walking
- I am unable to walk

SELF-CARE

- I have no problems washing or dressing myself
- I have slight problems washing or dressing myself
- I have moderate problems washing or dressing myself
- I have severe problems washing or dressing myself
- I am unable to wash or dress myself

USUAL ACTIVITIES (e.g. work, study, housework, family or leisure activities)

- I have no problems doing my usual activities
- I have slight problems doing my usual activities
- I have moderate problems doing my usual activities
- I have severe problems doing my usual activities
- I am unable to do my usual activities

PAIN / DISCOMFORT

- I have no pain or discomfort
- I have slight pain or discomfort
- I have moderate pain or discomfort
- I have severe pain or discomfort
- I have extreme pain or discomfort

ANXIETY / DEPRESSION

[figure not shown]
- I am not anxious or depressed
- I am slightly anxious or depressed
- I am moderately anxious or depressed
- I am severely anxious or depressed
- I am extremely anxious or depressed

Appendix 6: EQ-5D-5L

- We would like to know how good or bad your health is TODAY.
- This scale is numbered from 0 to 100.
- 100 means the best health you can imagine.
0 means the worst health you can imagine.
- Mark an X on the scale to indicate how your health is TODAY.
- Now, please write the number you marked on the scale in the box below.

YOUR HEALTH TODAY =

The best health
you can imagine

The worst health
you can imagine

USA (English) © 2009 EuroQol Group EQ-5D™ is a trade mark of the EuroQol Group

Appendix 7

Preexisting Autoimmune Diseases and Immune Deficiencies

Participants should be carefully questioned regarding their history of acquired or congenital immune deficiencies or autoimmune disease. Participants with any history of immune deficiencies or autoimmune disease listed in the table below are excluded from participating in the study. Possible exceptions to this exclusion could be participants with a medical history of such entities as atopic disease or childhood arthralgias where the clinical suspicion of autoimmune disease is low. Participants with a history of autoimmune-related hypothyroidism on a stable dose of thyroid replacement hormone may be eligible for this study. In addition, transient autoimmune manifestations of an acute infectious disease that resolved upon treatment of the infectious agent are not excluded (e.g., acute Lyme arthritis). Caution should be used when considering atezolizumab for participants who have previously experienced a severe or life-threatening skin adverse reaction or pericardial disorder while receiving another immunostimulatory anti-cancer agent. The Medical Monitor is available to advise as needed.

Autoimmune Diseases and Immune Deficiencies


 • Acute disseminated encephalomyelitis • Addison disease • Ankylosing spondylitis • Anti-phospholipid antibody syndrome • Aplastic anemia • Autoimmune hemolytic anemia • Autoimmune hepatitis • Autoimmune hypoparathyroidism • Autoimmune hypophysitis • Autoimmune myelitis • Autoimmune myocarditis • Autoimmune oophoritis • Autoimmune orchitis • Autoimmune thrombocytopenic purpura • Behçet disease • Bullous pemphigoid • Chronic fatigue syndrome • Chronic inflammatory demyelinating polyneuropathy • Churg-Strauss syndrome 	
 • Crohn disease • Dermatomyositis • Diabetes mellitus type 1 • Dysautonomia • Epidermolysis bullosa acquisita • Gestational pemphigoid • Giant cell arteritis • Goodpasture syndrome • Granulomatosis with polyangiitis • Graves disease • Guillain-Barré syndrome • Hashimoto disease • IgA nephropathy • Inflammatory bowel disease • Interstitial cystitis • Kawasaki disease • Lambert-Eaton myasthenia syndrome • Lupus erythematosus • Lyme disease, chronic • Meniere syndrome • Mooren ulcer • Morphea 	
 • Multiple sclerosis • Myasthenia gravis • Neuromyotonia • Opsoclonus myoclonus syndrome • Optic neuritis • Ord thyroiditis • Pemphigus • Pernicious anemia • Polyarteritis nodosa • Polyarthritits • Polyglandular autoimmune syndrome • Primary biliary cholangitis • Psoriasis • Reiter syndrome • Rheumatoid arthritis • Sarcoidosis • Scleroderma • Sjögren syndrome • Stiff-Person syndrome • Takayasu arteritis • Ulcerative colitis • Vitiligo • Vogt-Koyanagi-Harada disease
---	---	---

Appendix 8 Anaphylaxis Precautions

These guidelines are intended as a reference and should not supersede pertinent local or institutional standard operating procedures.

REQUIRED EQUIPMENT AND MEDICATION

The following equipment and medication are needed in the event of a suspected anaphylactic reaction during study treatment administration in a clinical setting:

- Monitoring devices: ECG monitor, blood pressure monitor, oxygen saturation monitor, and thermometer
- Oxygen
- Epinephrine for intramuscular (preferred route), subcutaneous, intravenous, or endotracheal administration in accordance with institutional guidelines
- Antihistamines
- Corticosteroids
- Intravenous infusion solutions, tubing, catheters, and tape

PROCEDURES

In the event of a suspected anaphylactic reaction during study treatment administration, the following procedures should be performed:

1. Stop the study treatment administration, if possible.
2. Call for additional medical assistance.
3. Maintain an adequate airway.
4. Ensure that appropriate monitoring is in place, with continuous ECG and pulse oximetry monitoring if possible.
5. Administer antihistamines, epinephrine, or other medications and IV fluids as required by participant status and as directed by the physician in charge.
6. Continue to observe the participant and document observations.

Appendix 9

Risks Associated with Atezolizumab and Guidelines for Management of Adverse Events Associated with Atezolizumab

Although *toxicities* observed with atezolizumab have been mild and self-limiting, *they* should be recognized early and treated promptly to avoid potential major complications. Discontinuation of atezolizumab may not have an immediate therapeutic effect, and in severe cases, immune-mediated toxicities may require acute management with topical corticosteroids, systemic corticosteroids, or other immunosuppressive agents.

DOSE MODIFICATIONS

There will be no dose modifications for atezolizumab in this study.

TREATMENT INTERRUPTION

Atezolizumab treatment may be temporarily suspended in participants experiencing toxicity considered to be related to study treatment. *Management guidelines for patients who experience adverse events associated with atezolizumab are provided in [Table 1](#).* Atezolizumab treatment may be suspended for reasons other than toxicity (e.g., surgical procedures). The acceptable length of treatment interruption must be based on the investigator's benefit–risk assessment and in alignment with the protocol requirements for the duration of treatment and documented by the investigator. The Medical Monitor is available to advise as needed.

Table 1 Dose Modification and Management Guidelines for Patients Who Experience Adverse Events Associated with Atezolizumab

GENERAL GUIDANCE

Early Recognition and Close Monitoring:

Patients and family caregivers should receive timely and up-to-date information prior to initiating therapy and throughout treatment and survival follow-up. There should be a high level of suspicion that new symptoms are treatment related. Irrespective of severity grade, patients presenting with adverse events should be monitored closely and referred promptly to specialists for evaluation. Initiate treatment as per institutional guidelines and supportive care measures as deemed necessary.

Adverse Event Management Guidance—Use of Corticosteroids and/or Immunosuppressants:

For Grade 1 events, atezolizumab therapy should be continued with close monitoring of the affected organ function (including but not limited to TSH, liver function tests, blood glucose, creatinine, urine protein, amylase, and lipase), with exceptions specified below. For Grade ≥ 2 events, initiate treatment with high-dose corticosteroids (1–2 mg/kg/day oral prednisone/IV methylprednisolone or equivalent) as clinically indicated (see the table below). If symptoms do not improve within 48 hours of high-dose corticosteroid use, other immunosuppressants may be considered. If corticosteroids have been initiated, they must be tapered over ≥ 1 month to the equivalent of ≤ 10 mg/day oral prednisone before atezolizumab can be resumed. For toxicities not described below, refer to the current standard clinical practice/management guidelines of immune checkpoint inhibitor-related toxicities including but not limited to those provided by a professional society (e.g., NCCN, ESMO, SITC, and ASCO).

Action to be Taken with Atezolizumab:

For Grade 1 events, atezolizumab therapy should be continued. Consider withholding atezolizumab for most Grade 2 toxicities unless specified below. Withhold for all Grade 3 toxicities. Permanently discontinue for Grade 4 toxicities, with the exception of endocrinopathies that are controlled by hormone-replacement therapy. Atezolizumab can be withheld for up to 12 weeks after event onset. If atezolizumab is withheld for >12 weeks, the patient should be discontinued from atezolizumab. However, atezolizumab may be withheld for >12 weeks to allow for patients to taper off corticosteroids prior to resuming treatment.

For events, symptoms, and/or laboratory values that resolve to Grade 1 or better, resume atezolizumab. For events that do not resolve to Grade 1 or better while withholding atezolizumab, permanently discontinue atezolizumab and contact the Medical Monitor. Resumption of atezolizumab may be considered in patients who are deriving benefit and have fully recovered from the immune-mediated event, with exceptions listed below. The decision to rechallenge patients with atezolizumab should be based on the investigator's benefit-risk assessment and documented by the investigator. The Medical Monitor is available to advise as needed.

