Appendix 9: Management of Adverse Events Associated with Atezolizumab

Event	CTCAE Toxicity Grade or Condition	Action to be Taken with Atezolizumab	Adverse Event Management [guidance in addition to the general recommendations provided above]
Pulmonary event	Grade 1	
 For pneumonitis, consider withholding and resuming on radiographic evidence of improvement. 	
 Re-evaluate on serial imaging.
	Grade 2	
 Withhold. 	
 Consider bronchoscopy or BAL with or without transbronchial biopsy. Initiate treatment with high-dose oral corticosteroids, followed by taper.
	Grade 2 recurrent/not improving after 48–72 hours of corticosteroids or Grades 3–4	
 Permanently discontinue. In case of pneumonitis, atezolizumab should not be resumed after permanent discontinuation. 	
 Oral or IV broad-spectrum antibiotics should be administered in parallel to the immunosuppressive treatment. Bronchoscopy or BAL with or without transbronchial biopsy is recommended. Initiate treatment with high-dose IV corticosteroids, followed by taper when event resolves to Grade 1 or better. If event does not improve, consider adding an immunosuppressive agent.
Hepatic event	Guidelines for patients without hepatocellular carcinoma		
	Grade 2	
Events of >5 days' duration:
 
 Withhold. 	
All events:
 
 Monitor LFTs more frequently until return to baseline values. 
Events of >5 days' duration:
 
 Initiate treatment with high-dose oral corticosteroids.

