Appendix 9: Management of Adverse Events Associated with Atezolizumab

	Grades 3–4	
 Permanently discontinue. 	
 Consider liver biopsy to establish etiology of hepatic injury. Initiate treatment with high-dose oral corticosteroids, followed by taper when event resolves to Grade 1 or better. If event does not improve, consider adding an immunosuppressive agent.
Guidelines for patients with hepatocellular carcinoma			
	
AST/ALT is within normal limits at baseline and increases to $>3 \times \text{ULN}$ to $\leq 10 \times \text{ULN}$ or AST/ALT is $> \text{ULN}$ to $\leq 3 \times \text{ULN}$ at baseline and increases to $>5 \times \text{ULN}$ to $\leq 10 \times \text{ULN}$ or AST/ALT is $>3 \times \text{ULN}$ to $\leq 5 \times \text{ULN}$ at baseline and increases to $>8 \times \text{ULN}$ to $\leq 10 \times \text{ULN}$
	
 Withhold. If event resolves to baseline or to Grade 1 or better, resume. If event does not resolve to baseline or to Grade 1 or better while withholding, permanently discontinue and contact the Medical Monitor. 	
 Monitor LFTs more frequently until return to baseline values. For events of >5 days' duration, consider initiating treatment with high-dose oral corticosteroids.
	AST or ALT increases to $>10 \times \text{ULN}$ or	
 Permanently discontinue. 	
 Consider liver biopsy to establish etiology of hepatic injury. Initiate treatment with high-dose oral corticosteroids, followed by taper when event resolves to baseline.

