Appendix 9: Management of Adverse Events Associated with Atezolizumab

Hypophysitis (pan-hypopituitarism)	Grades 2–3	
 • Withhold. 	
 • Perform brain MRI (pituitary protocol). • Initiate treatment with high-dose IV corticosteroids and convert to oral corticosteroids upon improvement, followed by taper. • Initiate hormone replacement if clinically indicated.
	Recurrent hypophysitis or Grade 4	
 • Permanently discontinue. 	
Ocular event	Grade 1	
 • Continue. 	
 • Initiate treatment with topical corticosteroid eye drops and topical immunosuppressive therapy.
	Persistent Grade 1 despite treatment or Grade 2	
 • Withhold. 	
	Grades 3–4	
 • Permanently discontinue. 	
 • Initiate treatment with high-dose oral corticosteroids, followed by taper when event resolves to Grade 1 or better.
Myocarditis or pericardial disorders	Grades 2–4	
 • Permanently discontinue. • Atezolizumab should not be resumed after permanent discontinuation. 	
 • Consider anti-arrhythmic drugs, temporary pacemaker, ECMO, VAD, or pericardiocentesis as appropriate. • Initiate treatment with higher-dose IV corticosteroids equivalent to 1 g/day IV methylprednisolone for 3–5 days and convert to high-dose oral corticosteroids upon improvement, followed by taper when event resolves to Grade 1 or better. • If event does not improve within 24 hours after initiating corticosteroids, consider adding an immunosuppressive agent.

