Appendix 9: Management of Adverse Events Associated with Atezolizumab

Amylase and/or lipase elevation	Grade 2 with amylase and/or lipase >1.5–2.0 × ULN	
 • Continue. 	
 • For prolonged elevation (e.g., >3 weeks), consider treatment with corticosteroids equivalent to 10 mg/day oral prednisone, followed by taper.
	Grade 2 asymptomatic with amylase and/or lipase >2.0–5.0 × ULN or Grades 3–4	
 • Withhold. • For recurrent events, permanently discontinue. 	
 • If no improvement, consider treatment with high-dose oral corticosteroids, followed by taper.
Pancreatitis	Grades 2–3	
 • Withhold. • For recurrent events, permanently discontinue. 	
 • Initiate treatment with high-dose IV corticosteroids and convert to oral corticosteroids upon improvement, followed by taper.
	Grade 4	
 • Permanently discontinue. 	
 • Initiate treatment with high-dose IV corticosteroids and convert to oral corticosteroids upon improvement, followed by taper when event resolves to Grade 1 or better. • If event does not improve, consider adding an immunosuppressive agent.
Dermatologic event	Grade 1	
 • Continue. 	
 • Consider treatment with topical corticosteroids and/or other symptomatic therapy (e.g., antihistamines).
	Grade 2		
 • Consider biopsy, if indicated. • Initiate treatment with topical corticosteroids. • Consider treatment with higher-potency topical corticosteroids if the event does not improve. • If unresponsive to topical corticosteroids, consider oral prednisone 0.5 mg/kg/day.

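### Appendix 9 tells investigators to withhold for every Grade 3 toxicity, but 11 of the 21 graded event categories in the same table require permanent discontinuation at Grade 3

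*Protocol*

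**What the plan says.** Protocol Sections 4.3.2, 5.1 and 5.1.1 send investigators to Appendix 9 for managing toxicity, including when to interrupt or stop atezolizumab. Table 1 of that appendix opens with general guidance and then lists event-specific rows.

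The general paragraph on drug action sets a rule for each grade:

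- **Grade 2:** consider withholding for most events, expressly subject to what the rows below specify.
- **Grade 3:** "Withhold for all Grade 3 toxicities". No qualification follows.
- **Grade 4:** "Permanently discontinue for Grade 4 toxicities, with the exception of endocrinopathies that are controlled by hormone-replacement therapy".

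The next paragraph deals with restarting: "For events, symptoms, and/or laboratory values that resolve to Grade 1 or better, resume atezolizumab". It then adds a discretionary rule: "Resumption of atezolizumab may be considered in patients who are deriving benefit and have fully recovered from the immune-mediated event, with exceptions listed below".

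The rows give their own actions. For Grade 3–4 hepatic events in patients without hepatocellular carcinoma, the action is "Permanently discontinue". For Grade 2–4 myocarditis or pericardial disorders it is the same, with the addition "Atezolizumab should not be resumed after permanent discontinuation". The Grade 3–4 pulmonary row also requires permanent discontinuation and adds "In case of pneumonitis, atezolizumab should not be resumed after permanent discontinuation". For amylase or lipase elevation at Grades 3–4 the action is to withhold, followed by "For recurrent events, permanently discontinue".

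**The concern.** Withholding and permanent discontinuation are different actions in this table. The first leads to restarting once the event has settled. The second ends treatment, subject at most to a discretionary rechallenge. An investigator who takes the general Grade 3 sentence at its word would withhold for a Grade 3 hepatitis, nephritis or pneumonitis and restart at Grade 1. The row for each of those events says to stop. With roughly 40–50 sites (Section 3.1.1), two sites could treat the same event differently and each cite Table 1.

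The sentences around the Grade 3 rule make its wording stand out. The Grade 2 sentence defers to the rows and the Grade 4 sentence carries its own exception. The Grade 3 sentence says *all*.

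**Working it through.** The documents state no count of their own, so the check is a tally of the event rows in Appendix 9, Table 1, classed by the action for a first Grade 3 event.

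**Denominator.** The table has 22 event categories. Suspected HLH carries no grade, so 22 − 1 = 21 categories cover Grade 3. The hepatic category is counted by its entries for patients without hepatocellular carcinoma, because the hepatocellular entries are defined by multiples of the upper limit of normal rather than by grade. Rows that apply at any grade count as covering Grade 3.

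**Permanent discontinuation at Grade 3:**

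- Eight categories name Grade 3 by number or within a range: pulmonary, hepatic, ocular, myocarditis/pericardial, neuropathy, myelitis, renal, and infusion-related reaction/cytokine release syndrome (IRR/CRS).
- Three apply at any grade: confirmed Stevens-Johnson syndrome/toxic epidermal necrolysis (SJS/TEN), myasthenia gravis/Guillain-Barré syndrome, and meningoencephalitis.
- Total: 8 + 3 = 11.

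**Withholding at Grade 3:** diarrhea/colitis, hypothyroidism, hyperthyroidism, adrenal insufficiency, hyperglycemia, hypophysitis, amylase/lipase elevation, pancreatitis, dermatologic events, and a first Grade 3 myositis. Total: 10.

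**Result.** 11 + 10 = 21, and 11/21 = 52.4% of categories depart from the general Grade 3 rule.

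**Sensitivity to the counting rule:**

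| Convention | Count | Share |
|---|---|---|
| Only categories naming Grade 3 (21 − 3 = 18) | 8/18 | 44.4% |
| SJS/TEN counted by its suspected entry (withhold) | 10/21 | 47.6% |
| IRR/CRS left out, because Appendix 9 footnote c grades it on the ASTCT scale | 10/20 | 50.0% |
| IRR/CRS left out and only categories naming Grade 3 | 7/17 | 41.2% |
| Ungraded suspected HLH added | 12/22 | 54.5% |

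Under every convention the unqualified rule fails for a large share of the table.

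**Grade 4 rule.** The general sentence exempts only endocrinopathies controlled by hormone replacement. Amylase/lipase elevation is not an endocrinopathy. Its Grades 3–4 entry says withhold and reserves permanent discontinuation for recurrence, so a first Grade 4 elevation gets opposite instructions. The endocrine rows that withhold at Grade 4 are taken here as falling under the rule's own exception.

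**Precedence.** No sentence ranks the rows above the general drug-action rules. The management column is headed as adding to the general recommendations. The drug-action column has no such label, so the headings do not settle the question.

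**The case against.** The strongest reply is that specific rows override general guidance in any table laid out like this. The missing qualifier proves little by itself. The general corticosteroid guidance gives the Grade 1 rule subject to exceptions, the drug-action paragraph repeats it without them, and the Grade 1 pneumonitis entry still departs from it. The text plainly does not repeat its deferral every time. Section 4.6.1 separately requires discontinuation for intolerable toxicity, and Section 4.3.2.1 advises against continuing after a toxicity linked to atezolizumab by either route. All of this stands, and it limits the point to wording. It does not make the sentence correct: the rule says *all*, and the precedence has to be inferred.

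Three stronger readings are tempting, and the documents do not support them.

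- **Resumption is left open in five categories.** A reader might note that six of the 11 categories carry an explicit bar on resumption (pulmonary for pneumonitis only), while hepatic, ocular, neuropathy, renal and IRR/CRS do not. The discretionary resumption sentence and the row-specific bars together support two tiers: discontinuation with possible rechallenge after a documented benefit-risk assessment, and discontinuation with none. Hepatic, ocular, neuropathy and renal events fit the first tier. Extending it to IRR/CRS is an inference, since that sentence speaks of immune-mediated events.
- **Footnote g contradicts its own row.** It is attached to permanent discontinuation for Grade 3 and 4 IRR/CRS, yet describes premedication for later infusions. Its second sentence applies a benefit-risk test like the one in the general guidance, so it can be read as instructions for a rechallenge. It could be clearer, but a contradiction is not shown.
- **Suspected SJS/TEN conflicts with the Grade 4 rule.** That entry is provisional pending specialist confirmation. It also refers to the dermatologic rows, where Grade 4 means permanent discontinuation.

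**Conclusion.** The point holds as an internal inconsistency in a patient-safety instruction. The general Grade 3 sentence is wrong as written for 11 of the 21 graded categories, and the general Grade 4 sentence is wrong for one row, amylase/lipase elevation. The count rests on the conventions set out in the working.

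The percentage describes rows of a table, not patients or risk. The number of participants who could be affected cannot be derived from the documents. A reader might infer that the protocol permits routine re-dosing after serious immune-mediated events. It does not: following the event row is the natural reading, and the safeguards in the main text remain. No effect on the primary preference analysis follows. The correction is worth making because it is cheap and the instruction concerns when to stop treatment.

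**What to change.** In the drug-action paragraph of Appendix 9, Table 1:

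1. Change the Grade 3 sentence to *Withhold for Grade 3 toxicities unless specified below*.
2. Add *unless specified below* to the Grade 4 sentence, which also accommodates the amylase/lipase row.
3. Add one sentence stating that event-specific rows take precedence over the general drug-action text.

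Optionally, open footnote g with *If re-treatment is considered after benefit-risk assessment*.

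The cost is a few words at the next amendment, with no change to data collection or analysis. The Protocol's amendment summary says these guidelines were aligned with Investigator's Brochure Version 20, which was not available for this review. The sponsor should check whether that wording needs the same correction, so that the two documents stay aligned.
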